11.1 Estimated Sample Size

One of the study goals is to identify consistent efficacy trends in the primary and key secondary endpoints. Twenty-five subjects per group will generate 70% power to detect the effect size of 0.6 at the 0.1 two-sided significance level. This sample size will also be sufficient to generate 80% power to detect the effect size of 0.82 at the 0.05 two-sided significance level. Accounting for a 10%-13% drop-out rate, approximately 28 subjects per group were initially planned. No data are available on the CDM1-RS instrument. Based on the preliminary data observed in the AMO-02-MD-2-001 study, the assumed effect sizes look reasonable. The effect size assumptions are partially based on the Clinician VAS total score changes from baseline to end of study (6 points on drug vs. 1 point on placebo with the common standard deviation of 5.8). Based on these and other data, 29 and 22 subjects per group will be sufficient to generate 90% and 80% power at the 0.05 two-sided significance level. Based on these calculations, the suggested sample size of 56 patients total was considered adequate to detect the treatment effect or at least a consistent trend.

A blinded SSRE, based on the observed variance in the primary outcome measure, was performed during the conduct of the study. Based on the blinded SSRE, the planned sample size is sufficient to detect the treatment difference between active and control arms based on the primary endpoint with at least 80% power at the 0.05 two sided significance level. However, the variability of the key secondary endpoint was slightly greater than that originally assumed. Respectively, it was recommended, if operationally feasible, to increase the total sample size to a maximum of 66 subjects.

However, based on the blinded SSRE, the pooled standard deviation of change from baseline for the primary endpoint was 2.64. Assuming this standard deviation and as long as the difference in the primary endpoint mean change from baseline to EOT between drug and control is at least 2.2, the power to detect treatment differences will be 82% if n=25/group.

The details of the SSRE and summary of scenarios and outcomes are outlined in the SAP.

Investigational Medicinal Product: Tideglusib

Protocol No: AMO-02-MD-2-003 AMO Pharma Ltd.

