3 SAMPLE SIZE

Twenty-five subjects per group will generate 80% power to detect the effect size of 0.82 at the 0.05 two-sided significance level. This sample size will also be sufficient to generate 70% power to detect the effect size of 0.6 at the 0.1 two-sided significance level. Accounting for a 10%-13% drop-out rate, approximately 28 subjects per group will be enrolled.

No data are available on the CDM1-RS instrument. Based on the preliminary data observed in the AMO-02-MD-2-001 study, the assumed effect sizes look reasonable. The effect size assumptions are partially based on the Clinician VAS total score changes from baseline to end of study (6 points on drug vs. 1 point on placebo with the common standard deviation of 5.8). Based on these and other data, and subjects per group will be sufficient to generate 90% and 80% power at the 0.05 two-sided significance level. Based on these calculations, the suggested sample size of 56 subjects total is adequate to detect the treatment effect or at least a consistent trend.

A blinded sample size re-estimation will be performed, per FDA guidance on adaptive designs (Section IV, Adaptive designs based on non-comparative data), once subjects have been enrolled and have completed Visit All study subjects, investigators, site staff and Sponsor's staff and delegates (including the statistical consultant and SQN staff) will remain blinded to treatment assignments.

The blinded sample size re-estimation will be conducted based on the observed standard deviation in the change from baseline in the clinician-completed CDM1-RS at EOT in the ITT population in those subjects who have completed Visit . Summary statistics (mean, median, standard deviation, minimum and maximum) and histograms of the observed values and change from baseline will be provided by visit up to Visit with all subjects being presented under an 'Overall' treatment group. This summary will provide an estimate of the pooled standard deviation for evaluation. Similar summaries will be provided for the clinician-completed CGI-I and the Top 3 Caregiver Concerns VAS score. The blinded external statistical consultant will then conduct the sample size scenarios.

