No data on treatment effect and variability based on the CDM1-RS instrument are available; the estimates of mean changes from baseline are not available for placebo, or for the active treatment arm. Three initial scenarios are pre-specified here (treatment effect $\Delta = 5.0, \, \Delta = 3.6, \, \text{and} \, \Delta = 2.1$). However, the clinical relevance of these assumptions is unknown. Additional scenarios will be based on the observed standard deviation and additional assumed treatment differences. Scenarios involving the CGII and/or the Top 3 Caregiver Concerns VAS score may also be assessed. The decisions regarding corresponding sample size increases will be made based on these estimates and other considerations.

Dependent upon the blinded estimate of standard deviation, the sample size may be increased to ensure 80% power for a chosen treatment effect. Any increase in sample size will be limited to 2 times the maximum of the initial sample size. Additional (not pre-specified) scenarios may be requested by the Sponsor after pre-specified scenarios have been reviewed based on various assumptions regarding effect size.

Sample size update due to SSRE

Based on the blinded SSRE, the planned sample size is sufficient to detect the treatment difference between active and control arms based on the primary endpoint with at least 80% power at the 0.05 two-sided significance level. However, the variability of the key secondary endpoint was slightly greater than that originally assumed. Respectively, it was recommended, if operationally feasible, to increase the total sample size to 66 subjects. Further details are in Appendix 2.

As it was not operationally feasible to enroll 66 subjects, 53 subjects were randomized. Sample size calculations based on SSRE results supported this operational decision.

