4 RANDOMIZATION

Randomization will occur in a 1:1 manner (e.g. 1000 mg weight adjusted tideglusib: placebo) such that each treatment group will have approximately 28 children and adolescents contributing data to the primary efficacy analysis, stratified by age group,

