6.13 Efficacy Evaluation

Unless specified otherwise, all listings will be based on the RIS set.

All efficacy analyses and summaries will be primarily performed on the ITT analysis set. Summaries of run-in efficacy data will also be performed on the RIS set. The analysis for the primary and key secondary estimands will be repeated on the FAS and the PPS sets. The sensitivity analyses of the primary and the key secondary estimands will be based on the ITT set only. All other efficacy analyses will be based on the ITT set only.

All hypothesis tests comparing tideglusib and placebo will be two-sided and conducted at the 5% significance level, unless otherwise specified.

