6.13.1.1 Primary Estimand and Supplementary Analysis

The estimand for the primary efficacy endpoint is the difference between group adjusted means in the changes from baseline in CDM1-RS total score at EOT.

If a subject's in-clinic visit is unavailable, the data will be imputed with the corresponding telehealth assessment. The use of telehealth assessments is thought unlikely to be related to outcome, however, it will be assessed for balance between the treatment groups and sensitivity analyses may be conducted in the event of imbalance.

The null hypothesis being tested for the primary endpoint is that there is no difference in mean change in CDM1-RS total score from baseline to EOT between the tideglusib and placebo treatment groups:

$$H_0$$
: Mean Change_{tideglusib} = Mean Change_{placebo}

The alternative hypothesis is that there is a difference in either direction in the mean change in CDM1-RS total score from baseline to EOT between the tideglusib and placebo treatment groups:

$$H_1$$
: Mean Change_{tideglusib} \neq Mean Change_{placebo}

The analysis will include data from Visit (randomisation) to Visit (EOT) inclusive. Data from other visits will be included in the summaries and listings.

Primary Analysis

The primary estimand will be analysed using a mixed model for repeated measures (MMRM).

The treatment difference between tideglusib and placebo at Visit (EOT) will be estimated as the simple contrast in the treatment effect. The standard error (SE), p-value and 2-sided 95% confidence interval (CI), based on the difference in the Least Squares (LS) means between the two treatment groups will be presented. The LS Means, SE and 95% CI will additionally be presented for each treatment by visit.

The MMRM model will be implemented using restricted maximum likelihood (REML). The Kenward-Roger approximation will be used to estimate the denominator degrees of freedom and standard errors

Initially an unstructured covariance matrix will be investigated. If this analysis fails to converge, the following alternative structures will be tested in the following order until convergence is achieved: Toeplitz, AR(1) and compound symmetry. If a covariance matrix other than unstructured is selected, the estimated standard errors and variance-covariance matrix of the fixed-effects parameters will be computed using a robust "sandwich" estimator (i.e., by specifying the EMPIRICAL option on the PROC MIXED statement).

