6.13.2.1 Key Secondary Estimand and Supplementary Analyses

The estimand for the key secondary efficacy endpoint is the difference between treatments in the observed CGI-I score at EOT. Any data collected after study discontinuation will not contribute to the treatment effect estimation.

If a subject's in-clinic visit is unavailable, the data will be imputed with the corresponding telehealth assessment.

The null hypothesis being tested for the key secondary estimand is that there is no difference in CGI-I at EOT between the tideglusib and placebo treatment groups:

$$H_0$$
: $MeanCGI - I_{tideglusib} = MeanCGI - I_{placebo}$

The alternative hypothesis is that there is a difference in either direction in the CGI-I at EOT between the tideglusib and placebo treatment groups:

$$H_1$$
: $MeanCGI - I_{tideglusib} \neq MeanCGI - I_{placebo}$

The analysis will include data from Visit (randomisation) to Visit (EOT) inclusive. Data from other visits will be included in the summaries and listings.

Key Secondary Analysis

The key secondary estimand will be analysed using a MMRM.

The treatment difference between tideglusib and placebo at EOT will be estimated as the simple contrast in the treatment effect. The 2-sided 95% confidence interval (CI), based on the difference in the Least Squares (LS) means between the two treatment groups will be presented. The LS Means (and 95% CI) will additionally be presented for each treatment by Visit.

The MMRM model will be implemented using REML. The Kenward-Roger approximation will be used to estimate the denominator degrees of freedom and adjust standard errors.

Initially an unstructured covariance matrix will be investigated. If this analysis fails to converge, the following alternative structures will be tested in the following order until convergence is achieved: spatial spherical, spatial power, spatial Gaussian and compound symmetry. If a covariance matrix other than unstructured is selected, the estimated standard errors and variance-covariance matrix of the fixed-effects parameters will be computed using a robust "sandwich" estimator (*i.e.*, by specifying the EMPIRICAL option on the PROC MIXED statement).

The model will contain treatment, age group, visit and treatment by visit interaction as fixed effects, baseline CGI-I as a covariate.

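### If the unstructured MMRM does not converge, the fallback's uncorrected sandwich SE runs the nominal 5% test at about 6–7% with 53 children

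*SAP*

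**What the plan says.** SAP 6.13.1.1 fits the primary MMRM by REML and states its inference method without tying it to one covariance structure: "The Kenward-Roger approximation will be used to estimate the denominator degrees of freedom and standard errors". The unstructured matrix is tried first. On non-convergence the order is Toeplitz, then AR(1), then compound symmetry (CS), none of them named in a version with visit-specific variances. Whenever one of these is used, the SEs and the fixed-effects covariance matrix come from a sandwich estimator, "by specifying the EMPIRICAL option on the PROC MIXED statement". No bias-corrected form of the sandwich is named, and no df rule is given for the fallback.

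SAP 6.13.2.1 has the same SE rule for CGI-I but a different list of structures: "spatial spherical, spatial power, spatial Gaussian and compound symmetry". SAP 6.13 states that the tideglusib–placebo tests "will be two-sided and conducted at the 5% significance level". On size, SAP 3 records: "As it was not operationally feasible to enroll 66 subjects, 53 subjects were randomized".

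**The concern.** Kenward-Roger enlarges a model-based covariance matrix and chooses df to suit a small sample. Once the sandwich replaces that matrix, the adjustment has nothing to act on. The classical sandwich is built from fitted residuals, which are on average smaller than the true errors, so it is biased downward when independent units are few. The fallback therefore loses its small-sample protection, and the SAP does not say which reference distribution applies.

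At stake is the p-value that carries the trial's claim. Under SAP 6.14, significance on CGI-I may be claimed only if the primary analysis is significant at 5%, so an inflated primary test loosens that gate as well. The same MMRM is reused in the multiple-imputation sensitivity analyses, the subgroup and single-item analyses, and the other secondary endpoints.

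**Working it through.** **Inputs from the documents**
- Two-sided 5% level (SAP 6.13).
- 53 randomized (SAP 3). "Randomization will occur in a 1:1 manner" (SAP 4), so taken as 27 and 26.
- "Accounting for a 10%-13% drop-out rate" (SAP 3); 11.5% used.
- Protocol 11.1: "the pooled standard deviation of change from baseline for the primary endpoint was 2.64"; used as the SD at end of treatment.
- Mean model: treatment, age group, visit, treatment by visit, baseline (SAP 6.13.1.1).

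**Assumptions**
- 3 or 5 post-baseline visits (redacted).
- AR(1) correlation of 0.7 between adjacent visits.
- Either a constant SD, or an SD that doubles from the first to the last visit.
- Monotone drop-out, completely at random.
- Satterthwaite df stand in for Kenward-Roger df (single contrast).

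**Step 1. The plan's own figure.** Protocol 11.1 gives 82% power for a difference of 2.2 with 25 per group. The effect size is 2.2/2.64 = 0.833 and the noncentrality is 0.833 × √(25/2) = 2.95. On 48 df the noncentral t gives 82.3%; the normal approximation gives 83.8%. The stated figure is reproduced. The documents give no achieved type I error for the fallback, only the nominal 5%.

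**Step 2. Analytic approximation.** Take four mean parameters at the final visit: intercept, treatment, age group and baseline. The uncorrected sandwich SE is then too small by a factor of about √((53 − 4)/53) = √(49/53) = 0.96. The actual error is P(|T₄₉| > 0.9615 × c), where c is the critical value used:
- t on 49 df: c = 2.01, threshold 1.93, error 5.9%
- t on 150 df: c = 1.98, threshold 1.90, error 6.3%
- normal: c = 1.96, threshold 1.88, error 6.5%

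**Step 3. Simulation under the null.** 10,000 trials per setting (Monte Carlo SE about 0.25 points), REML fits under CS, AR(1) and Toeplitz, testing the end-of-treatment contrast. The mean sandwich SE was 0.73–0.75 against a true SD of the estimate of 0.76–0.77. The ratio ran from 0.7355/0.7682 = 0.957 to 0.7497/0.7741 = 0.968, so about 3–4% too small. Ranges below cover the three structures and both visit counts.

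| SE and reference distribution | Type I error |
|---|---|
| Classical sandwich, Kenward-Roger-type df (median 85–132) | 5.9–6.6% |
| Classical sandwich, residual df | 6.1–6.8% |
| Classical sandwich, normal | 6.2–6.9% |
| Classical sandwich, t on 49 df | 5.7–6.3% |
| Leverage-corrected sandwich (CR2), t on 49 df | 5.0–5.4% |
| Jackknife-type sandwich (CR3), t on 49 df | 4.3–4.6% |
| Model-based, equal-variance structure, constant SD | 5.0–5.5% |
| Model-based, equal-variance structure, SD doubling | 12.6–13.9% |

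The sandwich rows cover both SD patterns. With Kenward-Roger-type df the error was 5.9–6.5% under constant SD and 6.4–6.6% under doubling SD, so the variance pattern contributes little.

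**Step 4. Alternative structures.** In a separate simulation, heterogeneous AR(1) and Toeplitz with model-based SEs on 49 df (standing in for Kenward-Roger) gave 4.7–5.9%. The corrected sandwich on 49 df gave 4.9–5.9% there, and the uncorrected one about 6–7.5%.

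**The case against.** **The fallback may never be reached.** Unstructured covariance with Kenward-Roger is the main route, and it is sound. Trial fits with 53 subjects, 3, 5 or 8 visits, correlation 0.5 to 0.9 and rounded scores gave 0 convergence failures in 1,080. That was not the trial's software, and the seven-category CGI-I was not simulated. This stands: the inflation is conditional on non-convergence. A reader might infer that the primary analysis as a whole runs above 5%; the documents do not support that.

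**The sandwich is a safeguard.** Pairing a simple structure with a robust SE is a recognised protection against a wrong covariance. This stands too. A reader might blame the equal-variance structures, but the error is much the same whether variances are equal or growing, and the sandwich is what prevents the 12.6–13.9% in Step 3. The weakness is only that the sandwich is uncorrected and its df unstated.

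**The specific sentence overrides the general one.** On this reading the sandwich rule simply replaces the Kenward-Roger SE, and there is no conflict. That is reasonable, but the df rule is then still missing, and every rule tried gave more than 5%.

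**Size.** A reader might infer a larger error. A simulation with 1,500 trials per structure gave 7.3–7.5% for AR(1) but only 5.3–5.4% for Toeplitz, the first fallback, with a Monte Carlo SE of 0.6 points. The larger run gave at most 6.9% for any structure or df rule.

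**Visit spacing.** A reader might infer that Toeplitz and AR(1) are wrong because visits are unequally spaced, since CGI-I uses spatial structures. The visit weeks are redacted, so unequal spacing cannot be shown. The two lists do differ without explanation.

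**Partial cover.** Wilcoxon tests with Hodges-Lehmann intervals are planned for both endpoints and do not use the sandwich. They are sensitivity analyses and do not correct the primary p-value.

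**Conclusion.** The point holds as a conditional one. If the unstructured fit fails, the SAP's rule gives an SE about 3–4% too small, and a nominal 5% test runs at about 6–7%, an excess of roughly 1 to 2 points. The error was anticonservative under every df rule, structure and variance pattern in the larger simulation, so this is a wrong error bar in the fallback and more than missing detail. It is not a large error.

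The size rests on 53 children, 3 or 5 visits, the assumed correlation and SD patterns, and reading EMPIRICAL as the classical uncorrected form. How the software combines EMPIRICAL with Kenward-Roger is not in the documents, hence the range of df rules. For CGI-I the conclusion follows from the identical SE rule. CS is on both lists, but the spatial structures and the ordinal scale were not simulated.

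**What to change.** State one SE and one df rule for the fallback, in the same words in SAP 6.13.1.1 and 6.13.2.1. Either option works:

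- **(a)** Keep the fallback structures, but use a small-sample-corrected sandwich (leverage-corrected CR2 or Mancl-DeRouen type) with t df based on the number of children, such as 53 − 4 = 49. CR2 restored 5.0–5.4%; the jackknife-type version was slightly conservative at 4.3–4.6%.
- **(b)** Use heterogeneous Toeplitz, then heterogeneous AR(1), then heterogeneous CS, with model-based Kenward-Roger SEs and df and no EMPIRICAL. Heterogeneous CS was not itself simulated.

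Do not simply delete EMPIRICAL while keeping the equal-variance structures.

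The SAP addendum of 22 August 2024 documents post-hoc analyses, so the primary model may already have been run. In that case, report which structure converged for each endpoint. If it was unstructured, nothing changes. If it was a fallback, add the corrected SE as a sensitivity analysis.

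The cost is a few lines of SAP text and code, and slightly wider intervals if the fallback is used.
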